APPENDIX IV: SCHEDULE OF EVENTS

PROCEDURE/TEST	Baseline	Pre-Procedure (within 24 hours)	Procedure	Post-Procedure	1 month (28-35d) Office visit ³	3 month (90±7d) Office visit or phone contact ⁴	6 month (180± 14d) Office visit or phone contact ⁴	12 month (365± 28d) Office visit or phone contact ⁴	Unscheduled visits
Subject Medical/Clinical History (Age, Sex, Risk Factors, Cardiac Status, Cardiac History)	✓								
Subject Informed Consent (Must be obtained prior to any trial related testing or procedures) ¹	✓								
General Inclusion/Exclusion Criteria	✓								
Angiographic Inclusion/Exclusion Criteria			✓						
Coronary Angiogram			✓						
Stent and Procedure Information			✓						
Antiplatelet Medications Loading Dose		✓ ⁵	✓ ⁵	✓ ⁵					
P2Y12 Inhibitor Discontinuation Eligibility Assessment					✓				
Post-procedure Antiplatelet Medications ²					✓	✓	✓	✓	✓
Adverse Events					✓	✓	✓	✓	✓

¹ Consenting after the index procedure but prior to hospital discharge (or up to 3 days after the index procedure) is acceptable, only if the site confirms that the protocol required DAPT regimen is site's standard of care.

[figure not shown]
² Subject who are "1-month clear" will discontinue P2Y12 inhibitor as early as 28 days, but continue taking aspirin through 12-month follow-up. Subjects who are not eligible for early P2Y12 inhibitor discontinuation will be treated per site standard of care.

³ A formal office visit is required at 1-month follow-up to ensure a thorough clinical evaluation. A telephone contact is an option *only* for subjects who would otherwise be lost to follow-up due to being unable to complete an office visit, but a formal follow-up visit is still preferred at 1-month.

⁴ Office visit is strongly recommended whenever possible.

⁵ It is recommended that the antiplatelet medication loading dose be given before the procedure (within 24 hours prior to procedure), at time of procedure, or post-procedure (recommended to be within 1 hour post-procedure).

APPENDIX V: CLINICAL TRIAL FLOW

¹ Consenting after the index procedure but prior to hospital discharge (or up to 3 days after the index procedure) is acceptable, only if the site confirms that the protocol required DAPT regimen is site's standard of care.

² A formal office visit is required at 1-month follow-up to ensure a thorough clinical evaluation. A telephone contact is an option *only* for subjects who would otherwise be lost to follow-up due to being unable to complete an office visit, but a formal follow-up visit is still preferred at 1-month.

³ "1-month clear" is defined as subjects who are free from myocardial infarction (modified ARC), repeat coronary revascularization, stroke, or stent thrombosis (ARC definite/probable) within 1 month (prior to 1-month visit but at least 28 days) after stenting AND have been compliant with 1-month dual antiplatelet therapy (DAPT) without interruption of either aspirin and/or P2Y12 receptor inhibitor for > 7 consecutive days.

⁴ Office visit is strongly recommended whenever possible

APPENDIX VI: MONITORING PLAN

A copy of the Monitoring Plan can be obtained upon request from the Clinical Project Manager for the trial.

[REDACTED]

[REDACTED]

The figure consists of a 3x9 grid of horizontal bars. The first two columns each contain 3 bars, while the third column contains 7 bars. All bars are black and of varying lengths. The grid is bounded by a white border.

1. SYNOPSIS OF STUDY DESIGN AND PROCEDURES

1.1 Purpose of the Statistical Analysis Plan

This statistical analysis plan (SAP) is intended to provide a detailed and comprehensive description of the planned methodology and analysis to be used for Protocol ABT-CIP-10271 the XIENCE 28 USA clinical study. This plan is based on the [REDACTED], December 4, 2018 study protocol.

1.2 Study Objectives

Primary Objective: to show non-inferiority of the primary endpoint of all death or all MI (modified ARC) from 1 to 6 months following XIENCE implantation in HBR subjects treated with 1-month dual antiplatelet therapy (DAPT) compared to a historical control after propensity score adjustment.

Secondary Objective: To show superiority of the major secondary endpoint of major bleeding (Bleeding Academic Research Consortium [BARC] type 2-5) from 1 to 6 months following XIENCE implantation in HBR subjects treated with 1-month DAPT compared to a historical control after propensity score adjustment.

1.3 Study Design

XIENCE 28 USA Study is a prospective, single arm, multi-center, open label trial to evaluate the safety of 1-month (as short as 28 days) DAPT in subjects at high risk of bleeding (HBR) undergoing percutaneous coronary intervention (PCI) with the approved XIENCE family of coronary drug-eluting stents.

The XIENCE family stent systems include FDA approved XIENCE Xpedition Everolimus Eluting Coronary Stent System (EECSS), XIENCE Alpine EECSS and XIENCE Sierra EECSS which are all manufactured by Abbott Vascular, Inc. The above listed XIENCE stents will hereinafter be called "XIENCE" in this trial. For each geography included in the trial (US and Canada), only approved and commercially available XIENCE stent(s) in that geography will be used.

A minimum of 640 subjects to a maximum of 800 subjects from approximately 50 sites in the United States (US) and Canada will be registered in this trial. Subject registration is capped at 75 per site. Trial population consists of non-complex HBR subjects with up to three native coronary artery lesions (a maximum of two lesions per epicardial vessel) with reference vessel diameter between 2.25 mm and 4.25 mm. Eligibility of P2Y12 receptor inhibitor discontinuation will be

assessed at 1-month follow-up. Subjects who are free from myocardial infarction (modified ARC), repeat coronary revascularization, stroke, or stent thrombosis (ARC definite/probable) within 1 month (prior to 1-month visit but at least 28 days) after stenting AND have been compliant with 1-month DAPT without interruption of either aspirin and/or P2Y12 receptor inhibitor for > 7 consecutive days are considered as “1-month clear” (refer to Section 1.4 for two exceptions), and will discontinue P2Y12 receptor inhibitor as early as 28 days and continue with aspirin monotherapy through 12-month follow-up.

All registered subjects will be followed at 1, 3, 6 and 12 months post index procedure.

The data collected from the XIENCE 28 USA Study will be pooled with the data from the XIENCE 28 Global Study (Protocol # ABT-CIP-10235) to compare with the historical control of non-complex HBR subjects treated with standard DAPT duration of up to 12 months from the XIENCE V USA Study, which is a US post-approval study to evaluate the safety of XIENCE V EECSS in “all-comer” population under real-world setting. The XIENCE V USA Study has been completed with a total of 8040 subjects enrolled, of which, ~1400 subjects were identified as non-complex HBR subjects who match the selection criteria of the XIENCE 28 USA Study. The XIENCE 28 Global Study is another AV-sponsored prospective, single arm study to evaluate the safety of 1-month DAPT in HBR subjects undergoing PCI with XIENCE. The XIENCE 28 Global Study is currently ongoing and plans to register at least 800 subjects globally outside US. The XIENCE 28 Global Study and the current XIENCE 28 USA Study share similar study design regarding inclusion/exclusion criteria, DAPT treatment strategy and follow up schedule, which supports the pooling of the two trial results.

1.3.1 Selection of Control

The XIENCE V USA historical HBR control is derived based on the following criteria:

Definition of non-complex HBR from XIENCE V USA

- HBR inclusion criteria (any one of the below HBR criteria):
 - Age \geq 75 years
 - History of major bleeding
 - History of stroke
 - Receiving or scheduled to receive chronic anticoagulation therapy
 - Renal insufficiency (creatinine > 2 mg/dl)
 - Anemia (Hb < 11 g/dl or transfusion)
 - Thrombocytopenia (platelet count $< 100.000/\text{mm}^3$)
- Exclusion criteria for non-complex:
 - STEMI
 - LVEF $< 30\%$

- Patients with more than 3 lesions treated during index procedure
- Patients with more than 2 vessels treated during index procedure
- At least one lesion with RVD < 2.25 mm or > 4.25 mm (visual estimation)
- At least one lesion located in left main
- At least one lesion located in graft
- At least one CTO lesion
- At least one in-stent restenosis lesion
- At least one target lesion with length > 32 mm by visual estimation.

The above selection criteria for the XIENCE V USA historical control aligns with the key inclusion/exclusion criteria of the XIENCE 28 USA Study.

For primary analysis, the XIENCE V USA non-complex HBR control subjects must be also 1-month clear, following the same logic as defined for the primary analysis population (refer to Section 1.4).

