5.3.2 *Angiographic Eligibility Criteria*

All angiographic eligibility criteria are based on visual assessment.

5.3.2.1 *Angiographic Inclusion Criteria*

1. Up to three target lesions with a maximum of two target lesions per epicardial vessel.
Note:
 - The definition of epicardial vessels means left anterior descending coronary artery (LAD), left circumflex coronary artery (LCX) and right coronary artery (RCA) and their branches. For example, the subject must not have >2 lesions requiring treatment within both the LAD and a diagonal branch in total.
 - If there are two target lesions within the same epicardial vessel, the two target lesions must be at least 15 mm apart per visual estimation; otherwise this is considered as a single target lesion.
2. Target lesion must be located in a native coronary artery with visually estimated reference vessel diameter between 2.25 mm and 4.25 mm.
3. Exclusive use of XIENCE family of stent systems during the index procedure.
4. Target lesion has been treated successfully, which is defined as achievement of a final in-stent residual diameter stenosis of <20% with final TIMI-3 flow assessed by online quantitative angiography or visual estimation, with no residual dissection NHLBI grade \geq type B, and no transient or sustained angiographic complications (e.g., distal embolization, side branch closure), no chest pain lasting > 5 minutes, and no ST segment elevation > 0.5mm or depression lasting > 5 minutes.

5.3.2.2 *Angiographic Exclusion Criteria*

1. Target lesion is in a left main location.
2. Target lesion is located within an arterial or saphenous vein graft.
3. Target lesion is restenotic from a previous stent implantation.
4. Target lesion is a chronic total occlusion (CTO, defined as lesion with TIMI flow 0 for at least 3 months).
5. Target lesion is implanted with overlapping stents, whether planned or for bailout.

Note: If there is more than one target lesion, all target lesions must satisfy the angiographic eligibility criteria. Non-target lesion (i.e., lesions that do not meet the angiographic criteria listed above) treatments are not allowed during the index procedure.

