6.2 Index Procedure

Only XIENCE stent can be used for target lesion(s). Stent implantation procedure should be performed according to the instruction for use (IFU) of the XIENCE family stent used. If XIENCE stent is delivered beyond the guide catheter but not implanted, the subject cannot be registered in the trial. If other DES was implanted, the subject cannot be registered in the trial.

In this trial, a maximum of three target lesions may be treated with a maximum of two target lesions per epicardial vessel. Non-target lesion (i.e., lesions that do not meet the angiographic eligibility criteria) treatments are not allowed during the index procedure.

Subjects may receive appropriate anticoagulation and other therapy according to standard hospital practice.

Overlapping stents are not allowed in the trial, whether planned or for bailout. Subjects who received overlapping stents cannot be registered in this trial. According to XIENCE IFU, the maximal lesion length that may be treated is 32mm for a single XIENCE stent.

Bifurcation lesions are allowed in this trial. However, subjects treated with double stenting of both the main vessel and the side branch cannot be registered in this trial.

Planned staged procedures are not allowed.

Lesion characteristics (lesion location, % diameter stenosis, TIMI flow, RVD, lesion length, thrombus presence, bifurcation or not, lesion complexity), device (device name, size, number of device implanted, bailout usage, overlapping stent) and procedural information (procedure time, access site, procedural anticoagulant and anti-thrombotic medications, any procedure complications) will be collected and recorded in eCRF.

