2.1.3 Propensity Score

Given that subjects in the two comparison groups (pooled 1-month DAPT arm vs XIENCE V USA historical control) are not randomized and thus may not have balanced baseline characteristics, the non-inferiority and superiority tests for 1-6 month period will be carried out through stratified analysis in the “1-month clear” population. The stratification will be performed through propensity scores (PS). For each individual a propensity score (i.e., predicted probability between 0 and 1) for group (pooled 1-month DAPT arm) membership will be calculated using logistics regression, with “group” as the outcome and baseline variables including demographic, lesion characteristics, and risk factors as the predictors. Subjects will be categorized into 5 groups based on the calculated propensity scores and their quintiles. Non-inferiority and superiority will then be carried out for the rate of the endpoint using the method described in sections below stratified by the propensity quintiles.

The propensity score modeling and design will be performed by an independent statistician who has no access to any outcome data of the XIENCE 28 USA study, XIENCE 28 Global study and the XIENCE V USA historical control for the integrity and interpretability of study results. The independent statistician will be blinded and have no access to clinical outcome and any follow-up information to avoid introducing bias into the analysis.

Per the recent publication by Yue et al²⁸ on two-stage study designs involving propensity score adjustment, the propensity score calculation results will subsequently be sent to the FDA for review and approval prior to performing the primary endpoint and major secondary endpoint analyses.

2.1.3-1 Propensity Score Variable List

Based on prior clinical experience and clinical research, below is the list of variables that are considered to be related to assignments modeling building:

- Gender
- Age
- Creatinine
- Chronic anticoagulant
- History of stroke
- History of major bleeding
- Platelet
- Hb
- BMI

- Hypertension
- Dyslipidemia
- Prior PCI
- Prior CABG
- Prior MI
- Multivessel disease
- Clinical presentation (ACS (NSTEMI, ACS unstable angina) vs. non-ACS)
- Diabetes
- ACC/AHA lesion complexity
- Total lesion length per patient
- RVD
- Diameter stenosis%
- Bifurcation
- Number of lesions treated
- Number of vessel treated
- Number of stents per patient
- Total stent length per patient
- Discharge P2Y12
- Paris bleeding score

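### The XIENCE V USA control filter omits the trial's bars on overlapping stents and double-stented bifurcations, so the SAP's claim that the criteria align is wrong on this point; any bias in the death/MI comparison is conditional and probably modest.

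*SAP*

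**What the plan says.** **Trial side.** Protocol 5.3.2.2 excludes a subject if "Target lesion is implanted with overlapping stents, whether planned or for bailout". The Protocol Summary repeats this item under its Key Exclusion Criteria heading, and Protocol 6.2 repeats it as a registration rule. Protocol 6.2 also allows bifurcation lesions but adds that "subjects treated with double stenting of both the main vessel and the side branch cannot be registered in this trial".

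**Control side.** SAP 1.3.1 lists ten exclusions that define a non-complex control: STEMI, low LVEF, more than three lesions, more than two vessels, reference diameter out of range, left main, graft, chronic total occlusion, in-stent restenosis and, last, "At least one target lesion with length > 32 mm by visual estimation". Neither overlapping stents nor two-stent bifurcation treatment appears. The section closes by asserting alignment: "The above selection criteria for the XIENCE V USA historical control aligns with the key inclusion/exclusion criteria of the XIENCE 28 USA Study". SAP 1.3 says of the 8040 XIENCE V USA subjects: "of which, ~1400 subjects were identified as non-complex HBR subjects who match the selection criteria of the XIENCE 28 USA Study".

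**Adjustment.** SAP 2.1.3 models the probability of belonging to the 1-month DAPT arm and stratifies on quintiles. The variable list includes "Number of stents per patient", number of lesions treated, total stent length, total lesion length, bifurcation and lesion complexity. It does not include overlap. An outcome-blinded independent statistician builds the score, and FDA reviews the result before the endpoint analyses. No trimming rule is visible.

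**The concern.** The trial asks whether 1-month DAPT is non-inferior to standard DAPT in the same kind of non-complex patient. A control treated with overlapping or double stents could not have been registered in XIENCE 28 USA. Stratification on a propensity score works only where both arms hold comparable subjects, and here the filter admits a type of control that the USA arm rules out by design.

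Two things are at stake. If these patients have more death/MI between 1 and 6 months, they raise the control rate alone, and the non-inferiority test becomes somewhat too easy to pass. And even if their risk is the same, the stated ~1400 overstates the number of controls who meet the trial's criteria, and the lowest stratum of both the death/MI and the bleeding test may be short of test subjects. None of the visible sensitivity analyses (quartiles, antiplatelet compliance, the XIENCE 90 comparison, missing outcomes) examines this.

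**Working it through.** **Step 1: the texts side by side.**

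| Treatment feature | XIENCE 28 USA | Control filter, SAP 1.3.1 |
|---|---|---|
| Overlapping stents, planned or bailout | Excluded (Protocol 5.3.2.2, 6.2) | Not mentioned |
| Main vessel and side branch both stented | Cannot be registered (Protocol 6.2) | Not mentioned |
| Lesion length over 32 mm | Beyond the stated maximum for a single stent (Protocol 6.2) | Excluded |

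The list in SAP 1.3.1 shows no redaction, so the omission can be read directly.

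**Step 2: the plan's own figures.** SAP 1.5 gives about 1,600 test and about 1,400 control subjects. The test figure is 800 + 800 (SAP 1.3: USA maximum plus Global minimum). The power calculation cannot be reproduced because the margin and event rates are redacted.

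**Step 3: bias before stratification.** Let q be the share of controls with overlap or double stenting, p the 1-6 month death/MI rate without it, and RR their relative risk. With no true difference between arms, the control rate is raised by

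bias = q × p × (RR − 1).

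All three inputs are assumptions. At p = 6% and RR = 1.5:
- q = 5%: 0.05 × 0.06 × 0.5 = 0.15 points
- q = 10%: 0.30 points
- q = 20%: 0.60 points

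At RR = 1 the bias is zero for any q. Over p = 4-8% and q = 5-20%, it is 0.1-0.8 points at RR 1.5 and 0.2-1.6 points at RR 2.

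**Step 4: bias after quintile stratification.** This was simulated with 1,600 test and 1,400 control subjects and no true effect. The logistic score used lesion count, stent count, total stent length and four further covariates unrelated to outcome, with the arm imbalance scaled by 0.1, 0.3 or 0.6 SD. Stratum weights are not visible in the SAP, so two choices were tried. Results at p = 6%, RR = 1.5:

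| q | Crude bias (points) | Residual, Mantel-Haenszel weights | Residual, stratum-size weights | Share of these controls in lowest quintile | Test subjects in that quintile (of 600) |
|---|---|---|---|---|---|
| 5% | 0.15 | 0.10-0.12 | 0.11-0.12 | 74-100% | 135-263 |
| 10% | 0.30 | 0.16-0.22 | 0.19-0.23 | 86-100% | 123-233 |
| 20% | 0.59-0.61 | 0.25-0.34 | 0.34-0.39 | 94-100% | 95-168 |

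At RR = 2 the residual is 0.20-0.77 points; at RR = 1 it is zero.

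**Step 5: effect on the error rate.** The protocol's 0.025 level is taken as one-sided. With an assumed margin m,

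SE = √[(p + m)(1 − p − m)/1600 + p(1 − p)/1400], and false non-inferiority rate = Φ(−1.96 + bias/SE).

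At p = 6% and m = 2.5 points, SE = √(0.085 × 0.915/1600 + 0.06 × 0.94/1400) = 0.0094. A bias of 0.1, 0.2 or 0.35 points gives 0.032, 0.040 or 0.056. Over margins of 2-3 points and rates of 4-8%, the ranges are 0.031-0.033, 0.038-0.044 and 0.051-0.065.

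**The case against.** **The claim of alignment is limited to key criteria.** This does not rescue it for overlap, which the Protocol Summary itself lists under Key Exclusion Criteria. Double stenting is a registration rule in the index-procedure text, so there the objection has more force; it still leaves unexplained the SAP 1.3 statement that the controls match the selection criteria.

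**The propensity score already carries the relevant variables.** This stands in part. In the simulation, stratification removed between about a fifth (0.15 to 0.12) and three fifths (0.60 to 0.25) of the crude bias, because collecting these controls in one stratum also confines their effect to it. A reader might infer that the score cannot help at all; the calculation does not support that.

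**The blinded design stage and FDA review would reveal a sparse stratum.** They might, and this is a real safeguard. But the reviewer is told that the criteria align, and no rule says what happens if they do not.

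**The control filter limits the effect, and may err the other way.** It drops lesions over 32 mm, and "the XIENCE V USA non-complex HBR control subjects must be also 1-month clear", which removes subjects with early MI, stent thrombosis or repeat revascularization. It also drops controls with more than two treated vessels, whereas the trial's limit of three lesions, at most two per vessel, permits three vessels. That difference could offset some of the bias. These points bear on size and net direction; they do not close the gap.

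**Half the test arm is Global.** The Global protocol is not among the documents, so the absence of an eligible counterpart can be asserted only for the USA study.

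**Conclusion.** The mismatch is established from the text: the trial bars both groups, the control filter removes neither, and the alignment sentence is wrong on this point.

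The consequences are conditional. A reader might infer that these controls do collect in the lowest quintile and do push the result toward non-inferiority. The first is likely but depends on the fitted model. The second needs a higher 1-6 month death/MI risk in these patients. The documents give neither that risk, nor the number of such controls, nor the score distribution. Under an assumed 6% rate, risk ratio of 1.5 and 5-20% share, the residual bias is about 0.1-0.4 points, which would move a 0.025 test to roughly 0.03-0.06 at an assumed 2.5-point margin. At a risk ratio of 1 nothing moves except the count of comparable controls and the balance of the lowest stratum.

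This should be corrected, chiefly because correction is cheap before the score is fixed. It does not by itself show that the primary comparison is invalid.

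**What to change.** Before the propensity model is fitted and sent to FDA:

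1. Add both exclusions to SAP 1.3.1. Use a direct overlap, bailout or two-stent flag if XIENCE V USA recorded one; the documents do not say. The test-arm case report form already records overlap and bailout use (Protocol 6.2).
2. If there is no such flag, use stents implanted exceeding lesions treated as a proxy, applied identically to both arms. It is only a proxy: lesions less than 15 mm apart in one vessel count as one target lesion (Protocol 5.3.2.1), and no visible text bars two separate, non-overlapping stents there. Applied to controls alone, it would create a new asymmetry.
3. Restate the control count.

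If the full control set stays primary, correct the alignment sentence, report the number and quintile distribution of these controls at the outcome-blinded stage, and pre-specify both stratified tests (death/MI and bleeding) without them as a named sensitivity analysis.

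**Cost.** No new patients are needed, and both counts are already propensity variables. Controls fall from 1,400 to 1,330, 1,260 or 1,120 at an assumed 5, 10 or 20%. As a guide to precision, take an unstratified normal approximation with no bias, a 6% rate in both arms and a 2.5-point margin. With 1,400 controls SE = √(0.0564/1600 + 0.0564/1400) = 0.00869, and power is Φ(0.025/0.00869 − 1.96) = 82%. With 1,120 controls SE = 0.00925 and power is 77%. That drop is the price of the smaller sample and should not be read as evidence of bias.

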TLR	target lesion revascularization
TLF	target lesion failure
TVF	target vessel failure
TVR	target vessel revascularization
UADE	unanticipated adverse device effect
ULN	upper limit of normal
US	United States
USADE	unanticipated serious adverse device effect

APPENDIX II: DEFINITIONS**CLINICAL ENDPOINT DEFINITIONS****DEATH (Per ARC Circulation 2007; 115: 2344-2351)**

All deaths are considered cardiac unless an unequivocal non-cardiac cause can be established. Specifically, any unexpected death even in patients with coexisting potentially fatal non-cardiac disease (e.g. cancer, infection) should be classified as cardiac.

Cardiac death:

Any death due to proximate cardiac cause (e.g. MI, low-output failure, fatal arrhythmia), unwitnessed death and death of unknown cause, all procedure related deaths including those related to concomitant treatment.

Vascular death:

Death due to non-coronary vascular causes such as cerebrovascular disease, pulmonary embolism, ruptured aortic aneurysm, dissecting aneurysm, or other vascular cause.

Non-cardiovascular death:

Any death not covered by the above definitions such as death caused by infection, malignancy, sepsis, pulmonary causes, accident, suicide or trauma.

MYOCARDIAL INFARCTION (MI)**MI Definition (Modified ARC)**

Patients present any of the following clinical or imaging evidence of ischemia:

- Clinical symptoms of ischemia;
- ECG changes indicative of new ischemia - new ST-T changes or new left bundle branch block (LBBB), development of pathological Q waves*;
- Imaging evidence of a new loss of viable myocardium or a new regional wall motion abnormality)

AND confirmed with elevated cardiac biomarkers** per ARC criteria (Circulation 2007; 115: 2344-2351):

- Periprocedural MI:
 - Within 48h after PCI: CK-MB >3 x URL or Troponin > 3 x URL with baseline value < URL
 - Within 72h after CABG: CK-MB >5 x URL or Troponin > 5 x URL with baseline value < URL
- Spontaneous MI (> 48h following PCI, > 72h following CABG): CK-MB > URL or Troponin > URL with baseline value < URL

* Pathologic Q waves may be defined according to the Global Task Force, Minnesota code, or Novacode

**The assessment of CK-MB is preferred over the assessment of troponin for the diagnosis of peri-procedural MI, if possible. Baseline biomarker value requiring before study procedure and presumes a typical rise and fall.

Electrocardiographic Classification

- **Based on Q-Wave**
 - **Q-wave MI [QMI]**

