1.3.2 Primary Endpoint

The primary endpoint is a composite rate of all death or all myocardial infarction (modified Academic Research Consortium [ARC]) from 1 month to 6 months.

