1.4 Analysis Populations

Primary Analysis Population

The primary analysis population includes “1-month clear” population, defined as subjects who are free from myocardial infarction (modified ARC), repeat coronary revascularization, stroke, or stent thrombosis (ARC definite/probable) within 1 month

The above defined “1-month clear” population will be pooled from the XIENCE 28 USA Study and XIENCE 28 Global Study for both the primary and major secondary endpoint analyses. In this SAP the term ‘pooled 1-month DAPT arm’ refers to subjects pooled from the XIENCE 28 USA Study and XIENCE 28 Global Study, unless otherwise specified.

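### The trial bars planned staged PCI but the visible XIENCE V USA control filter does not, so controls with a planned second PCI after month 1 can stay in the benchmark; the bias has one direction and an unknown, possibly negligible, size

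*SAP*

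**What the plan says.** Protocol 6.2 states: "Planned staged procedures are not allowed". The Index Procedure row of the Protocol Summary says the same.

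The comparator comes from a study described in SAP 1.3 as run "to evaluate the safety of XIENCE V EECSS in “all-comer” population under real-world setting". SAP 1.3.1 narrows it to non-complex patients at high bleeding risk. Its limits on the extent of treatment refer to the index procedure, for example "Patients with more than 2 vessels treated during index procedure". No item concerns a later planned PCI. The section then concludes: "The above selection criteria for the XIENCE V USA historical control aligns with the key inclusion/exclusion criteria of the XIENCE 28 USA Study".

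The month-1 condition also applies to the comparator: "For primary analysis, the XIENCE V USA non-complex HBR control subjects must be also 1-month clear". SAP 1.4 defines its event-free part as "free from myocardial infarction (modified ARC), repeat coronary revascularization, stroke, or stent thrombosis (ARC definite/probable) within 1 month", without separating planned from unplanned revascularization.

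On outcomes, SAP 1.3.2 reads: "The primary endpoint is a composite rate of all death or all myocardial infarction (modified Academic Research Consortium [ARC]) from 1 month to 6 months". The periprocedural part of the MI definition in Protocol Appendix II is "Within 48h after PCI: CK-MB >3 x URL or Troponin > 3 x URL with baseline value < URL", and it is not limited to the index PCI. The major secondary endpoint is BARC 2-5 bleeding over the same window. The only procedural exception in the BARC text of Appendix II concerns CABG.

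**The concern.** The two arms are compared on events between months 1 and 6. In XIENCE 28 USA, a PCI planned at the index procedure for that window is against the rules. In the comparator, nothing visible removes it. A second PCI carries its own risk of periprocedural MI and access-site bleeding. If some controls had one, those events raise the control rate of both tested endpoints for a reason unrelated to DAPT duration.

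A higher control rate makes non-inferiority on death/MI easier to show, and superiority on bleeding as well. These are the only two formal tests against the control. The propensity strata adjust for baseline characteristics. The gap here is a procedure allowed in one arm and barred in the other, so stratification cannot close it fully.

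**Working it through.** **Can a staged control reach the endpoint window?**

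1. Planned second PCI in month 1: the control has a repeat revascularization within 1 month, is not 1-month clear, and is dropped.
2. Planned second PCI after month 1: the control passes the month-1 rule and every visible item of SAP 1.3.1, and stays in.
3. A qualifying MI within 48 h of that PCI counts as MI. A qualifying access-site bleed counts as BARC 2-5. Both fall in the 1-6 month window.
4. The propensity list in SAP 2.1.3 has multivessel disease and the numbers of lesions, vessels and stents, but not staging. None of the sensitivity analyses in SAP 2.9 addresses it.

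**How large could it be?** There is no plan figure to reproduce, because the event rates and margin are redacted.

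Inputs from the documents:
- test arm about 1,600 and control about 1,400 (SAP 1.5)
- significance level 0.025 for the non-inferiority test (Protocol 9.4), taken as one-sided and assumed to apply to the superiority test too

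Inputs that are assumptions:
- control rate p of 6% for death/MI and 7% for bleeding
- share s of controls with a planned PCI after month 1
- event risk r per such procedure

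Formulas (normal approximation, unstratified, test-arm variance taken at p because the margin is not visible):
- inflation of the control rate: d = s × r
- SE = √[p(1−p)/1600 + (p+d)(1−p−d)/1400]
- false-positive rate = Φ(d/SE − 1.96)

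Example with p = 6% and d = 0.3 points: SE = √(0.06×0.94/1600 + 0.063×0.937/1400) = 0.880 points; d/SE = 0.341; Φ(−1.619) = 5.3%.

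| Endpoint (assumed rate) | s × r | d (points) | Extra events in 1,400 | False-positive rate |
|---|---|---|---|---|
| Death/MI (6%) | none | 0 | 0 | 2.5% |
| Death/MI (6%) | 3% × 3% | 0.09 | 1.3 | 3.2% |
| Death/MI (6%) | 3% × 10%, or 10% × 3% | 0.30 | 4.2 | 5.3% |
| Death/MI (6%) | 10% × 6% | 0.60 | 8.4 | 9.9% |
| BARC 2-5 (7%) | 3% × 3% | 0.09 | 1.3 | 3.1% |
| BARC 2-5 (7%) | 6% × 6% | 0.36 | 5.0 | 5.7% |
| BARC 2-5 (7%) | 10% × 6% | 0.60 | 8.4 | 9.2% |

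A wider grid (control rates 3-8%, s of 1-10%, r of 2-10%, common variance p(1−p) in both arms) gives d from 0.02 to 1.0 points, or 0.3 to 14 extra control events. The false-positive rate then runs from 2.6% to 36%. That spread shows how little the documents constrain the answer.

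**The case against.** The strongest reply is that no harm has been shown. Nothing in the documents says that any XIENCE V USA control had a planned PCI after month 1, how that study treated staging, or whether it counted such events. An all-comer label describes who was enrolled, not how procedures were scheduled. This stands, and it rules out several stronger readings.

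- A reader might infer that the benchmark is inflated. The documents show only that it can be.
- A reader might infer that the alignment sentence is false. It refers to key inclusion/exclusion criteria, while the staging bar sits in the index-procedure rules and not in the numbered eligibility lists. The sentence is incomplete on this point, not contradicted.
- A reader might infer that such events can occur in the control only. The bar is a conduct rule, and non-compliance with it would be a protocol deviation. Non-target lesions are barred from treatment only at the index procedure, so later PCI of them can occur in the test arm and its events count. The Global study, about half of the pooled arm, is described only as similar in its criteria.
- A reader might take 10% as the error rate. It needs about 10% of controls staged specifically after month 1, which no passage supports.

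Three further points stand in part. A periprocedural MI also needs clinical, ECG or imaging evidence of ischemia, which argues against high values of r. The procedural covariates in the propensity model bear on the tendency to be staged and may mitigate the gap, though they cannot remove it. SAP 1.4 and 2.2.1 are partly redacted, so handling there cannot be excluded. The list in 1.3.1 is nevertheless visible and silent.

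**Conclusion.** The point holds as an unclosed gap in control selection, not as a demonstrated bias. XIENCE 28 USA bars planned staged procedures, the visible control filter does not, and the 1-month-clear rule closes the gap for month 1 only. To the extent that controls were staged later, the error favours the 1-month arm in both formal tests.

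Its size cannot be fixed from the documents. A false-positive rate of about 3% to 10%, against 2.5%, follows from assumed inflation of 0.09 to 0.6 points, and every input except the sample sizes and the significance level is an assumption. At the low end it is about one event in 1,400 controls and negligible. About four extra events would double the nominal error for death/MI at the assumed 6% rate. It is worth closing because the remedy is cheap and the comparator data already exist.

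**What to change.** **Preferred.** In SAP 1.3.1, add *staged procedure planned at the index procedure* to the control exclusions where XIENCE V USA recorded it. Have the outcome-blinded statistician of SAP 2.1.3 apply it, from index-procedure data only, before the propensity design is fixed. Report how many controls it removes.

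**If it was not recorded.** State in 1.3.1 that this restriction of the trial could not be applied to the control, and report the number of controls with a PCI in months 1-6. Where the indication for those PCIs is available, add to SAP 2.9 one supportive run of each propensity-stratified test, identical in both arms. In that run, MI or BARC 2-5 bleeding within 48 h after an elective PCI of a lesion left untreated at index is not counted. Label it supportive only, because it may also drop some genuine events.

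**Cost.** SAP wording, and at most one extra run per endpoint. The fallback run needs PCI indications, which the documents do not show to exist for the control. The downside is the loss of a few controls, and a slightly less favourable contrast if staging was common. No treatment, visit or enrolment rule changes.
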